10.4.2 ANALYSIS OF THE PRIMARY ENDPOINTS

The following will be consider for the analysis primary endpoints:

The results of each Blinded Reviewer's evaluation of photographs taken at three and six moth compared to baseline will be analyzed and the results will be reported as a % of the correctly identified post treatment photographs chosen per Blinded Reviewer. An average of the % of the correctly identified post treatment photographs chosen by Blinded Reviewer will be calculated and used to determine

Bar, pie charts or graphs indicating percentages of the correctly identified post treatment photographs chosen by Blinded Reviewer may also be used to analyse efficacy.

The efficacy endpoint to treatment will be defined by an average of the 80% of the correctly identified post treatment photographs chosen by Blinded Reviewer This will be used to determine if the study meets the primary endpoint expectation.

The % of the correctly identified post treatment photographs chosen by Blinded Reviewer of all subjects who received at least one treatment of Venus Bliss™ and for whom at least one valid post-baseline assessment were obtained will be analysed for these primary endpoints. Mutiple imputation method or modelling of available data may be used for missing data as appropriate.

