7.3.5 EARLY TERMINATION VISIT

Subjects who terminate the study early for whatever reason, will be asked to provide a reason for their early termination. Adverse events and the reason for early termination will be recorded.

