10 STATISTICAL CONSIDERATIONS

10.1 STATISTICAL AND ANALYTICAL PLANS

The Statistical and Analytical Plans (SAP) may be revised during the study to accommodate Clinical Trial Protocol Amendments and to make changes to adapt to unexpected issues in study execution and data that affect planned analyses. If revised, a formal SAP will be completed and issued prior to database lock and unblinding of the study data.

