10.2 STATISTICAL HYPOTHESES

The null and alternative hypotheses for the study's primary, key secondary and safety endpoints are;

- Primary Efficacy Endpoints: Statistical hypothesis will not be applied in the analysis of the study's primary endpoint
- Secondary Efficacy Endpoint(s):
 - Null Hypothesis ($H_0: \mu_d = \mu_{post} - \mu_{baseline} = 0$) – There is no change in thickness of the adipose layer as measured by ultrasound (US) at twelve weeks post-treatment as compared to baseline.

Alternative Hypothesis ($H_a: \mu_d = \mu_{post} - \mu_{baseline} \neq 0$) – There is a change in thickness of the adipose layer as measured by ultrasound (US) at twelve weeks post-treatment as compared to baseline. The efficacy endpoint to treatment will be defined by reduction in abdominal fat determined by decrease in thickness of the adipose layer as measured by ultrasound (US) at twelve weeks post-treatment as compared to baseline.

- Null Hypothesis ($H_0: \mu_d = \mu_{post} - \mu_{baseline} = 0$) – There is no change in abdominal circumference at twelve weeks post-treatment as compared to baseline.

Alternative Hypothesis ($H_a: \mu_d = \mu_{post} - \mu_{baseline} \neq 0$) – There is a change in abdominal circumference at twelve weeks post-treatment as compared to baseline. The change will

be defined by reduction in abdominal circumference at twelve weeks post-treatment as compared to baseline.

- Null Hypothesis ($H_0: \mu_d = \mu_{post} - \mu_{pre} = 0$) – There is no satisfaction with the treatment at twelve weeks using the 5-Point Likert Subject Satisfaction Scale as assessed by the subjects.

Alternative Hypothesis ($H_a: \mu_d = \mu_{post} - \mu_{pre} \neq 0$) – There is satisfaction with the treatment at twelve weeks using the 5-Point Likert Subject Satisfaction Scale as assessed by the subjects.

- Safety Endpoint: Statistical hypothesis will not be used in the analysis of the study's safety endpoint.

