10.3 ANALYSIS DATASETS

The Intention-to-Treat Analysis Dataset will be used; efficacy and safety analyses will be carried out on all subjects who underwent Venus Bliss™ treatment.

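### Section 10.4.2 bases the primary analysis on three- and six-month photographs, but the endpoint is at twelve weeks, no six-month photograph is scheduled, and its analysis set conflicts with section 10.3

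*Combined protocol and SAP*

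**What the plan says.** **Time point.** The Protocol Summary, section 3 and section 4.2.1 place the primary endpoint at twelve weeks, and section 10.4.1 also compares outcome at twelve weeks with baseline. Section 10.4.2, which describes the primary analysis, says instead that each blinded reviewer's "evaluation of photographs taken at three and six moth compared to baseline will be analyzed".

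**Success rule.** Section 10.2 states: "Statistical hypothesis will not be applied in the analysis of the" primary endpoint. Section 10.4.2 defines efficacy by "an average of the 80% of the correctly identified post treatment photographs chosen by Blinded Reviewer". That sentence names no visit.

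**Analysis set.** Section 10.3 invokes intention to treat and says that "efficacy and safety analyses will be carried out on all subjects who underwent" the study treatment. Section 10.4.2 narrows this to treated subjects "for whom at least one valid post-baseline assessment were obtained will be analysed for these primary endpoints".

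**Missing data.** Section 10.4.2 adds: "Mutiple imputation method or modelling of available data may be used for missing data as appropriate".

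**The concern.** The text that should say how the primary result is produced calls for photographs that the study will not collect, and it does not name the twelve-week visit to which the endpoint is tied. Two sections then give different populations for the same result.

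With a hypothesis test, a loosely defined population would be one weakness among several. Here there is no test, and the study meets or misses its primary expectation by comparing one average with 80%. Whether a treated subject without a Week 12 pair is in the denominator, and how that subject is scored, can move the average across the line. If this is settled after the images have been read, the choice is open to the charge that it followed the result.

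**Working it through.** **1. Time points side by side.**

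- Endpoint: twelve weeks (Protocol Summary; sections 3 and 4.2.1; 10.4.1 agrees).
- Photographs: Visits 1, 2 and 3 (section 7.1.1), which are Day 0, Week 6 ± 3 days and Week 12 ± 7 days (sections 7.3.2 to 7.3.4 and the schedule of events table).
- End of participation: subjects are discharged at Visit 3 (section 7.3.4). Participant duration is three months (Protocol Summary).
- Primary analysis: three and six months (section 10.4.2).

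The last photograph within its window falls on day 84 + 7 = 91. Six months is about 182 days. Three months therefore fits Week 12, and six months fits no visit. The only other support for six months is a sentence in section 2.1, which says the study will look at whether effects last to six months. No visit serves that aim.

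**2. Analysis sets side by side.** Section 10.3 includes every treated subject. Section 10.4.2 drops any treated subject with no valid assessment after baseline. The two sets differ as soon as one such subject exists. On one reading, the 10.4.2 set also admits a subject who has a Week 6 photograph but no Week 12 pair, and the plan does not say how that subject would be scored.

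**3. What the denominator can do to the 80% rule.**

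Inputs from the documents: up to 50 subjects; 10% provision for loss (section 10.5, where 40 × 1.10 = 44); threshold 80% (section 10.4.2).

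Assumptions made here: one scored pair per subject; the 10% provision is realised as missing Week 12 pairs; the rule is read as at least 80%. The documents do not give the number of images per subject or the number of blinded reviewers.

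Let n be treated, m missing, o = n − m observed, p the observed average and c = p × o the number correct. Non-integer c is possible because the figure is an average over blinded reviewers.

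- Observed pairs only: c / o
- All treated, missing not correct: c / n
- All treated, missing imputed at the observed rate: (c + p × m) / n = p
- All treated, missing correct: (c + m) / n

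With p = 80%:

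- n = 50, m = 5, o = 45, c = 36: observed 36/45 = 80.0%; not correct 36/50 = 72.0%; imputed 40/50 = 80.0%; correct 41/50 = 82.0%.
- n = 44, m = 4, o = 40, c = 32: observed 32/40 = 80.0%; not correct 32/44 = 72.7%; imputed 35.2/44 = 80.0%; correct 36/44 = 81.8%.
- n = 50, m = 1, o = 49, c = 39.2: not correct 39.2/50 = 78.4%; correct 40.2/50 = 80.4%.
- m = 0: every rule gives 80.0%.

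If subjects with only a Week 6 photograph are admitted, the denominator in the first case lies between 45 and 50, depending on how many of the five have one.

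**The case against.** **The time-point error costs little.** Twelve weeks is stated repeatedly, including in section 10.4.1, so the intended primary comparison can be recovered. This stands. A reader might infer that the sponsor could choose between a three-month and a six-month result. The documents do not support that, because no six-month data will exist to choose. What remains is an analysis that cannot be carried out as written.

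**Week 6-only subjects may not be in the set at all.** The schedule of events table marks blinded review only at Day 0 and Week 12, so a valid assessment could mean the Week 12 review. That reading is reasonable. The row names the GAIS rather than image identification, so it does not settle the matter. The conflict between 10.3 and 10.4.2 remains on either reading.

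**Missing pairs may be few.** Section 5.4.1 asks for reasonable effort to contact lost subjects and retrieve data, and section 5.4.2 asks for every effort to hold a final visit and continue efficacy follow-up. For the early termination visit, section 7.3.5 says "Adverse events and the reason for early termination will be recorded"; it lists no photograph but forbids none. The number of missing pairs is therefore unknown.

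**The 72% to 82% spread uses rules the plan does not name.** This is correct. The plan names multiple imputation or modelling, and imputing at the observed rate returns 80.0%. A reader might take the spread as the likely effect, but it is only the outer limit. Nor is the plan silent on missing data: methods are named, and missing counts are reported under sections 10.4.1 and 10.4.6. The methods are optional, however, and a count does not say how a missing pair enters the 80% figure.

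**A later SAP can settle it.** Section 10.1 says "a formal SAP will be completed and issued prior to database lock and unblinding of the study data", but only if the plan is revised, and the deadline is not tied to image review.

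**Conclusion.** The point holds, and it rests on two contradictions in the text. The primary analysis in 10.4.2 names time points that do not match the twelve-week endpoint, and one of them matches no scheduled photograph. Sections 10.3 and 10.4.2 also give different analysis sets for the only primary success rule. Neither contradiction depends on any assumption.

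The size of the second is conditional. Under the assumptions stated, an observed 80.0% (36 of 45) can be anything from 72.0% to 82.0% of 50 treated subjects, and one missing pair in 50 is enough to put the worst case below 80%. With no missing pairs the choice of rule does not matter.

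It would go too far to infer that the endpoint cannot be identified, or that the reported result will be wrong. Twelve weeks is recoverable, and the amount of missing data is not known. The optional wording on imputation is missing detail rather than an error of its own. The phrase in section 3 about a proportion of reviewers, where 10.4.2 averages percentages of photographs over reviewers, is a minor alignment point.

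**What to change.** Before any image review:

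- **(a) Time point.** Reconcile sections 2.1 and 10.4.2 with the visit schedule. If no six-month visit is added, replace three and six months in 10.4.2 with twelve weeks (Visit 3), and tie the 80% rule to the pair formed by the baseline and Week 12 images.
- **(b) Analysis set.** State one primary set in identical words in 10.3 and 10.4.2, with one matching rule for Week 12 pairs that are missing or cannot be graded. If only observed pairs are scored, call the set evaluable pairs. If all treated subjects are scored, say how a missing pair is counted or imputed.
- **(c) Sensitivity analysis.** Repeat the 80% calculation over all treated subjects with missing pairs counted as not correct. The missing counts themselves are already planned.

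Section 3 can be aligned with the 10.4.2 measure in the same edit.

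Cost: wording changes, one extra table and a possibly less favourable reported figure. If the sponsor keeps the six-month aim in section 2.1, the cost is larger, since a visit and photographs would have to be added.

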10.4.3 ANALYSIS OF THE SECONDARY ENDPOINTS

For the analysis of changes in change in thickness of the adipose layer, abdominal circumference and subjects' assessment of satisfaction with the treatment secondary endpoints the following analysis will be considered:

Summary tables of changes in thickness of the adipose layer measured by ultrasound (US), abdominal circumference, and subjects' assessment of satisfaction at twelve weeks post-treatment as compared to baseline will be displayed as mean difference, standard deviation and standard error.

Bar charts, pie chart, graphs or any other descriptive statistical displays indicating scores, percentages and/or proportions of changes in thickness of the adipose layer measured by ultrasound (US), abdominal circumference, and subjects' assessment of satisfaction at twelve weeks post-treatment as compared to baseline will be used where applicable to analyse efficacy.

All statistical tests that will be two-sided. The level of statistical significance for effectiveness analyses is 5% ($\alpha = 0.05$) for all tests of differences. Where appropriate, two-proportion z-test will be used to compare the differences between of changes in thickness of the adipose layer measured by ultrasound (US), abdominal circumference, and subjects' assessment of satisfaction at twelve weeks post-treatment as compared to baseline. Analysis of Covariance (ANCOVA) may also be used where appropriate.

Change in thickness of the adipose layer measured by ultrasound (US), abdominal circumference, and subjects' assessment of satisfaction assessments at twelve weeks post-treatment as compared to baseline of all subjects who received at least one treatment of Venus Bliss™ and for whom at least one valid post-baseline assessment were obtained will be analysed for these secondary endpoints. Multiple imputation method or modelling of available data may be used for missing data as appropriate.

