4.2.2 SECONDARY ENDPOINTS

- To determine the change in thickness of the adipose layer as measured by ultrasound at twelve weeks post-treatment as compared to baseline
- To determine the change in abdominal circumference at twelve weeks post-treatment as compared to baseline
- To assess subject satisfaction with treatment at twelve weeks using the 5-Point Likert Subject Satisfaction Scale

Safety Endpoints:

- Report subject's assessment of discomfort and pain as measured by the Wong-Baker Faces Pain rating scale.
- Report subjects experiencing a treatment-related adverse event (AE).

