7 STUDY PROCEDURES AND SCHEDULE

7.1 STUDY PROCEDURES/EVALUATIONS

7.1.1 STUDY SPECIFIC PROCEDURES

The following procedures and evaluations will be done as part of the study:

Demographics

Medical / surgical history

Physical examination (as per site's standard of care)

Assessment of eligibility

Urine pregnancy test for women of child bearing potential (visit 1 only)

Treatment area marking

Abdominal circumference measurements

Photographs (visit 1, visit 2 and visit 3)

Ultrasound subcutaneous fat (visit 1, visit 2 and visit3)

Administration of a questionnaires/scales for patient-reported outcomes (visit 1 and visit 3 only)

Adverse event recording

Concomitant medications

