7.3.2 ENROLLMENT/BASELINE

Enrollment/Baseline/Treatment Visit (Visit 1 – Day 0)

Pre-Treatment

The investigator will confirm that the subject continues to meet the inclusion and none of the exclusion criteria. Adverse events, weight and any changes to concomitant medications will be recorded. The subject will complete the modified Simple Lifestyle Indicator Questionnaire (SLIQ).

The location and size of the treatment area will be left to the principal investigator's judgement based on his/her assessment of individual subject requirements for treatment. The defined abdominal treatment area will be marked with a semi-permanent pigment using a treatment template as per the sponsor's instructions. Photographs of the marked treatment area followed by ultrasound measurements of the marked treatment area will be made as per the instructions supplied by the sponsor. Measurement of the abdominal circumference will be made with the sponsor supplied tape measure using the marked boundaries as a guide for replication.

Treatment

Protective eye goggles will be worn by both the patient and site staff performing the treatment for the duration of the treatment session.

Based on the mild nature of treatment, anesthesia is not required. The treatment procedure should include positioning of the patient in a manner that enables access to the target treatment anatomical site.

The belt will be positioned on the subject as per the marked treatment template. Laser applicators will be secured in place by the belt with the areas treated for up to 25 minutes. The laser energy will be delivered to the area while cooling is administered to the skin surface to increase subject comfort. Treatment will continue until the total treatment area has been treated. The subject will receive one treatment session only.

The assessment of discomfort/pain during the treatment procedure will be assessed using the Wong-Baker Faces Pain rating scale with treatment parameters adjusted according to patient's comfort level.

Post Treatment

Assessment

The investigator will examine the treated areas and report immediate response (pain during treatment, hemorrhage, burn, erythema, edema, purpura) using a 5 point scale: 1=none; 2=trace; 3=moderate; 4=marked; 5=severe.

The assessment of discomfort/pain based on the subject's completion of the 10 cm visual pain scale should also be documented immediately after treatment.

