7.3.4 FINAL STUDY VISIT

Visit 3, Week 12 (\pm 7 days)

Subjects may return to the clinic twelve weeks after the treatment. Adverse events, weight and any changes to concomitant medications will be recorded.

Subjects will be asked to complete the lifestyle, 5-point Likert subject satisfaction and treatment evaluation questionnaires. Measurement of the abdominal circumference will be made with the sponsor supplied tape measure using the marked boundaries as a guide for replication.

Photographs of the marked treatment area followed by ultrasound measurements of the marked treatment area will be made as per the instructions supplied by the sponsor.

The End of Study form will be completed and subjects will be discharged from the clinic and terminated from the study.

The PI will record all reportable events with start dates occurring any time after informed consent is obtained until 7 (for non-serious AEs) or 30 days (for SAEs) after the last day of study participation.

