7.3.6 SCHEDULE OF EVENTS TABLE

Procedures	Screening (-6 weeks)	Enrollment/Treatment (Visit 1, Day 0)	Follow-up 1 Visit 2, Week 6 (± 3 days)	Follow-up 2 Visit 3, Week 12 (± 7 days)
Informed consent	X			
Inclusion/exclusion criteria	X	X		
Demographics	X			
Medical history	X			
Physical exam	X			
Weight		X	X	X
Urine pregnancy test ^a	X			
Lifestyle Indicator Questionnaire		X		X
Abdominal circumference		X	X	X
Photographs		X	X	X
Ultrasound subcutaneous fat		X	X	X
Administer Treatment		X		
Discomfort/Pain Visual Pain Scale		X		
PI immediate response		X		
Blinded reviewers GAIS		X		X
Subject satisfaction questionnaire				X
Treatment evaluation questionnaire				
Concomitant medication	X	X	X	X
Adverse event evaluation		X	X	X

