10.4 DESCRIPTION OF STATISTICAL METHODS

10.4.1 GENERAL APPROACH

This is an open-label, baseline-controlled, evaluator-blind multi-center study evaluating one treatment with a 1060 nm diode laser for non-invasive fat reduction of the abdomen.

All summary tables for quantitative parameters will display mean, standard deviation, median, range (minimum and maximum), percentages as well as number of missing data (if relevant). All summary tables for qualitative parameters will display counts, percentages and number of missing data if relevant. Baseline data are defined as the last photograph and measurement performed before the first treatment on Visit 1.

All statistical tests will be two-sided, where applicable. The level of statistical significance for effectiveness analyses is 5% ($\alpha = 0.05$) for all tests of differences. Where appropriate, t-test and/or two-proportion z-test will be used to compare outcome at twelve weeks post-treatment as compared to baseline. This test will enable us to accept or reject the null hypotheses. Rejection of null hypotheses will establish that:

- The two-sided 95% confidence interval for the difference between the means excludes zero.
- The two means are statistically significantly different at the 5% level ($P < 0.05$) two-sided.

Upon rejection of null hypotheses, further statistical test tools such as Confidence Interval, and/or One-way ANOVA and/or descriptive statistical tools may be used to determine the performance of the treatment.

In order to accommodate imbalances of some baseline of scores or measurements, covariate adjustment analysis may be performed in SAP to estimate adjusted treatment effects for the primary endpoint analysis.

The assumption for the statistical test is that variables are normally distributed within study group and the variation of scores or measurements at twelve weeks post-treatment as compared to baseline is not reliably different.

The safety analysis will be done by analyzing spontaneous reports of adverse events (AE), subjects' completed 10 cm discomfort/pain visual pain scale and immediate response reports by the principal investigator from his/her observation/examination of the treated area. Appropriate Medical Dictionary for Regulatory Activities (MedDRA) code will be used to describe all spontaneously reported or other study related adverse events.

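### The planned pre/post test of satisfaction has no baseline score to use, and the test listed for thickness and circumference does not fit them

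*Combined protocol and SAP*

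**What the plan says.** **Satisfaction.** Section 4.2.2 words the endpoint as a single-time assessment: "To assess subject satisfaction with treatment at twelve weeks using the 5-Point Likert Subject Satisfaction Scale". Section 10.2 sets a null on the post-minus-pre mean and puts it in words as "There is no satisfaction with the treatment at twelve weeks using the 5-Point Likert Subject Satisfaction Scale as assessed by the subjects". Section 10.4.3 then says that the subjects' "assessment of satisfaction at twelve weeks post-treatment as compared to baseline will be displayed as mean difference, standard deviation and standard error", and it repeats the comparison with baseline in its sentences on charts, tests and the analysed subjects. Section 10.4.1 fixes what baseline means: "Baseline data are defined as the last photograph and measurement performed before the first treatment on Visit 1".

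**Thickness and circumference.** Section 10.4.3 names a two-proportion z-test, to be used where it is appropriate, and an optional ANCOVA. Section 10.4.1 lists a t-test and/or a two-proportion z-test for week 12 against baseline, without saying that the t-test is paired. It adds an assumption that variation is similar at the two times. Section 10.5 uses a two-sample formula and refers to equal groups, although section 10.6.1 describes one non-randomized, baseline-controlled group.

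**The concern.** A difference from baseline needs a baseline value. If satisfaction is recorded only after treatment, the 10.2 hypothesis cannot be tested. The analyst would have to invent a reference value or abandon the test, possibly with the data in view. The multiple imputation allowed in 10.4.3 does not help, because it cannot supply a variable that nobody is scheduled to provide.

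For the two measured endpoints, the section devoted to them names a test for proportions from independent samples. The data are continuous, come in within-subject pairs, and have no defined cut-off that would yield proportions. The more suitable t-test appears only in the general section and its form is not fixed. What is at stake is prespecification of all three secondary endpoints and, for thickness, the width of the reported interval.

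**Working it through.** **1. Is there a pre-treatment satisfaction score?** The relevant places, side by side:

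| Place | What it provides |
|---|---|
| 7.3.2, Visit 1 before treatment | "The subject will complete the modified Simple Lifestyle Indicator Questionnaire (SLIQ"); no satisfaction scale |
| 7.3.4, Visit 3, week 12 | "Subjects will be asked to complete the lifestyle, 5-point Likert subject satisfaction and treatment evaluation questionnaires" |
| Schedule of Events Table, row "Subject satisfaction questionnaire" | one mark, in the week-12 column |
| 7.1.1 | "Administration of a questionnaires/scales for patient-reported outcomes (visit 1 and visit 3 only"); no questionnaire named |

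Only 7.1.1 could suggest a Visit 1 score. It is generic, and its pattern matches the lifestyle questionnaire, which the schedule marks at Visits 1 and 3. The specific visit text and the schedule agree with each other and outweigh it. Since 10.4.1 places baseline before treatment, a baseline satisfaction-with-treatment score would also have no meaning. Scheduled baseline scores: 0 of up to 50, so post minus pre is defined for no subject.

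**2. What is computable for satisfaction?** A week-12 distribution and a proportion. With 40 respondents and assumed counts, exact 95% intervals are: 20/40, 33.8% to 66.2%; 28/40, 53.5% to 83.4%; 36/40, 76.3% to 97.2%.

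**3. Does leaving out pairing matter for thickness?** Inputs from 10.5: expected reduction 2.65, SD 1.41 (units not stated), estimated sample size 40. The documents do not say whether 1.41 is the SD of the change or the SD at one visit, and they give no correlation rho between baseline and week 12. Both readings and a range of rho are therefore shown, assuming equal variance at the two visits, so that SD of change = per-visit SD × √(2(1 − rho)). Critical values: t(39) = 2.023 paired, t(78) = 1.991 unpaired.

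*Reading A, 1.41 is the SD of change*
- Paired half-width of the 95% CI: 2.023 × 1.41/√40 = 0.451.
- Unpaired: 1.991 × (1.41/√40)/√(1 − rho).

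*Reading B, 1.41 is the per-visit SD*
- Unpaired: 1.991 × 1.41 × √(2/40) = 0.628 at every rho.
- Paired: 2.023 × 1.41 × √(2(1 − rho))/√40.

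| rho (assumed) | A paired | A unpaired | B paired | B unpaired |
|---|---|---|---|---|
| 0.3 | 0.451 | 0.530 | 0.534 | 0.628 |
| 0.5 | 0.451 | 0.628 | 0.451 | 0.628 |
| 0.7 | 0.451 | 0.810 | 0.349 | 0.628 |
| 0.9 | 0.451 | 1.404 | 0.202 | 0.628 |

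In 40,000 simulated null trials with n = 40, the unpaired test rejected in 1.9%, 0.7%, 0.06% and 0.00% at these four values of rho, against about 5% for the paired test. In 20,000 simulated trials with a true change of 2.65 and rho from 0 to 0.9, power was 1.000 for both tests under both readings. An unpaired analysis would therefore be conservative and imprecise, but it would not miss an effect of the expected size.

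**4. Circumference.** The documents give no expected change or SD, so no figure is offered.

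**5. The stated 40.** The 10.5 inputs give (1.96 + 0.84)² × 1.41²/2.65² = 2.2 with a one-sample formula and twice that, 4.4 per group, with a two-sample formula. Neither reproduces 40; only the step 40 × 1.1 = 44 does. That is a separate matter, and nothing here depends on it.

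**The case against.** The best defence is that the satisfaction error is a drafting slip. The verbal null in 10.2 speaks only of week 12, the post-minus-pre notation repeats the lines above it, and 10.4.5 uses the same mean-difference phrase for a pain score taken after treatment. Counts and percentages for qualitative variables are already promised in 10.4.1, so most of a valid week-12 summary is in place. Section 10.1 also allows a revised SAP before database lock.

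This explains the error but does not remove it. The summary sentence in 10.4.3 carries no qualifier, and the hypothesis remains untestable. The SAP revision is optional.

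On thickness and circumference the defence is stronger. The tests are listed subject to being appropriate; 10.4.1 names a t-test and ties rejection to an interval for a difference of means; the notation in 10.2 defines a mean difference; and 10.4.3 summarises changes by mean difference, SD and SE. All of this points to a within-subject analysis. It stands that the plan does not choose an unpaired test. What remains is an unsuitable z-test, a missing statement of pairing, an assumption that a paired test does not need, and two-sample wording in 10.5. It is also fair that the half-width table describes a test the plan does not select, at correlations the documents do not give. It serves only to bound the effect.

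**Conclusion.** The concern holds. The satisfaction comparison is wrong as written: it cannot be computed for any subject. The endpoint definition itself is sound; the error lies in the 10.2 hypothesis and the 10.4.3 analysis. For thickness and circumference, the two-proportion z-test does not fit the data and the t-test is underspecified.

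This should be fixed, but it does not threaten the study's conclusion. The endpoints are secondary, and success rests on the 80% photograph criterion in 10.4.2. If an unpaired test were used for thickness, the 95% half-width at n = 40 would be 0.63 instead of 0.45 at an assumed rho of 0.5, with power near 100% either way. Those figures rest on the 10.5 inputs, equal variances and the assumed rho. The satisfaction finding rests on no numerical assumption.

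**What to change.** **Satisfaction**
- Delete the post-minus-pre hypothesis in 10.2 and the comparison with baseline in 10.4.3.
- Report the week-12 distribution and the proportion satisfied with an exact 95% CI. Prespecify from the scale's anchors, which the documents do not give, which categories count as satisfied.
- In 7.1.1, state which questionnaire is given at which visit.

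**Thickness and circumference**
- Remove the two-proportion z-test for these endpoints in 10.4.1 and 10.4.3.
- Name a paired t-test on week 12 minus baseline, with its 95% CI, as the main analysis, and drop the similar-variation assumption for it.
- Keep any ANCOVA as supportive, with covariates named in advance.
- In 10.5, align the two-sample and equal-group wording with the single-group paired design. This edit does not account for the 40.

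The cost is wording in 10.2, 10.4.1, 10.4.3 and 10.5 and one line in 7.1.1. No new data, visits or subjects are needed. The changes should be made before database lock and before the outcomes are examined.
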